8 ADVERSE EVENT REPORTING

Throughout the study, AEs will be recorded in the source documents and transcribed onto the appropriate pages of the eCRF regardless of whether the AEs are considered treatment-related. All AEs with onset dates from signature of the ICF through the end of the short term follow-up phase will be recorded as an AE on the eCRF. All SAEs with onset dates from signature of the ICF through the end of the short term follow-up phase must be recorded following the guidelines in Sections 8.6, 8.7, 8.8, 8.9 and 8.10. Any AE that occurs at any time after completion of the study, which the investigator considers to be related to

This document contains confidential information. It is intended solely for the use of the principal investigator, co-investigators, staff, appropriate institutional review boards or ethical committees, and other required regulatory bodies.

study drug, must be reported.

Conditions existing prior to screening will be recorded as part of the subject's medical history. To avoid confusion, the AE should be recorded in standard medical terminology. The Investigator is responsible for assessing the relationship of AEs to the IMP (Section 8.3).

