8.4 Recording of Adverse Events

All AEs encountered during the clinical study will be recorded in detail in the source documents and documented in the eCRF, from signature of the ICF through the end of the short term follow-up phase. All AEs that meet the seriousness criteria (Section 8.6) should

This document contains confidential information. It is intended solely for the use of the principal investigator, co-investigators, staff, appropriate institutional review boards or ethical committees, and other required regulatory bodies.

also be recorded on the SAE Report Form. All SAEs must be reported to the sponsor or delegated organization within the timeline stated in Section 8.7.

The recording of AEs will be based on data obtained from the following sources:

- Medical and surgical history
- Physical examinations including vital signs
- Clinical laboratory test results
- Subject diary

All clinical events, including both observed (such as any reaction at sites of application) and volunteered problems, complaints, or symptoms, are to be recorded. The need to capture this information is not dependent upon whether the clinical event is associated with the use of any IMP.

Clinical symptoms or events such as mucositis or stomatitis are not to be recorded as an AE or SAE.

Clinically significant bacteremia and clinical sepsis should be recorded as AE or SAE.

The potential adverse event profile of the IMP regimen is located in Appendix H.

If at anytime during the study a subject develops symptoms suggesting clinically significant bacteremia that can be attributed to sAGX0085 (as determined by three consecutive positive blood cultures), study treatment will be discontinued.

In the event that a subject develops symptoms suggesting clinically significant bacteremia or sepsis, the subject should be treated per the site's standard of care. Prior to treatment of the event, 3 consecutive whole blood samples need to be taken from the subject and aliquots of these samples must be sent immediately to Intrexon Actobiotics for analysis. The first two samples are to be drawn together and the third sample is to be drawn 10-15 minutes after the first tube is drawn. Detailed information can be found in the laboratory manual.

A disposition plan for the management of clinical sepsis is provided in appendix I.

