8.7 Reporting of Serious Adverse Events

The Sponsor is required to inform worldwide regulatory authorities of SAEs that meet specific criteria. Therefore, the Sponsor must be notified immediately regarding any SAE that occurs after informed consent is obtained. All SAEs and follow-up information must be reported within 24 hours after the investigator has gained knowledge of it, as required by local regulations, by faxing a completed SAE Report Form to the fax number below or emailing a completed SAE Report Form to the PSI Safety Desk at [contact].

Country	Toll-free Safety Line Numbers
Belgium	[name] [name] (Brussels) [name] (Antwerp)
Germany	[name]
US	[name] [name] [name]
ИК	[name]

Table 3: Toll-free Safety Line Numbers for SAE Reporting*

*Any fax sent to these lines will be routed to safety desk e-mail address ([contact])

This document contains confidential information. It is intended solely for the use of the principal investigator, co-investigators, staff, appropriate institutional review boards or ethical committees, and other required regulatory bodies.

The necessity and time requirements for reporting SAEs to the Sponsor or designee and regulatory agencies are as follows:

- All SAEs will be reported via the eCRF system within 24 hours of the investigator's first knowledge of the event, even if the event does not appear to be related to AG013. In case reporting via the eCRF is not available, the SAE may be reported via fax in order to meet the reporting requirements.
- Reports of any pregnancy in a subject, must also be reported on the Pregnancy Report Form within 24 hours of the investigator's first knowledge of the event (see section 8.6) and fax completed form to PSI Safety Desk or e-mail a scanned copy to [contact], even if no AE has occurred.
- For all SAEs, a detailed written description that includes anonymized copies of available relevant patient records, autopsy reports, and other documents will be sent within 24 hours of the investigator's first knowledge of the SAE.
- SAEs that are life threatening or result in death, and are unexpected and related to AG013 will be reported to regulatory authorities within 7 days of receipt of the event. Any follow up to the initial SAE report will be submitted to regulatory authorities within 8 days of the initial report (ie, within15 days of receipt of initial report).

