8.8 Serious Adverse Event Recording Period

SAEs will be collected and recorded by the Investigator beginning from the signature of the ICF through the end of the short term follow-up phase.

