11.4 Data Safety Monitoring Board

An independent DSMB will be constituted before the start of the study. The DSMB will supervise the ethical performance of the study and review safety data arising during the study according to the procedures described in the DSMB Charter. The Charter will describe the following activities:

- Committee membership
- Committee responsibilities
- Frequency and content of meetings
- Procedures for the review and assessment of the safety data of the first 10 subjects on AG013 having completed study treatment
- Procedures for the expedited review for clinically significant bacteremia and clinical sepsis
- Procedures for the review and assessment of the cumulative safety data
- Criteria for determining whether to recommend stopping the study for unacceptable harm.

The DSMB will be composed of 3 or more members who will have relevant experience in the treatment of subjects with OM and/or HNC and the conduct of randomized clinical trials. One member will be a biostatistician experienced in phase 2 and 3 oncology clinical trials, and none of the members will be Investigators in this study or employees of the sponsor . Any AE that leads to a subject's treatment termination, and any SAE a subject experiences during the study, will be regularly reported to the DSMB, as specified in the Charter. The DSMB will receive unblinded data for any subject in the case of these safety events.

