11.5 Financial Disclosure by Principal Investigators (if study under IND)

Since this is a "covered" clinical trial, the Investigator will ensure that 21 CFR §54 is adhered to. A "covered" clinical trial is any study of a drug or device in humans submitted in a marketing application or reclassification petition subject to this part that the applicant or the FDA relies on to establish that the product is effective (including studies that show equivalence to an effective product) or that make a significant contribution to the demonstration of safety. This requires that investigators and all sub investigators (inclusive of family members) provide documentation of their financial interest or arrangement with the Sponsor or proprietary interests in the drug being studied. This documentation must be provided prior to the participation of the Investigator and any Sub Investigator. The Investigator and Sub-Investigator agree to notify the Sponsor of any change in reportable interests during the study and for one year following completion of the study. Study

This document contains confidential information. It is intended solely for the use of the principal investigator, co-investigators, staff, appropriate institutional review boards or ethical committees, and other required regulatory bodies.

completion is defined as the date that the last subject has completed the protocol defined activities.

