12.9 End of Study

End of study is defined as the date when the last subject completes the long-term follow-up phase (i.e. 12 months after the last dose of CRT).

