4.3 DATA AND SAFETY MONITORING BOARD (DSMB)

An independent DSMB will be constituted before the start of the study. The DSMB will supervise the ethical performance of the study and review safety data arising during the study according to the procedures described in the DSMB Charter. To protect subjects from unanticipated safety risks, an initial safety analysis will be performed when enrolment and treatment in the double-blind study when 10 subjects on AG013 have been recruited. The DSMB will review safety data after these 10 subjects on AG013 have completed study treatment. The DSMB, per their Charter, will determine what, if any, changes to the study protocol or conduct are required.

The DSMB will be composed of 3 or more members who will have relevant experience in the treatment of subjects with OM and/or HNC and the conduct of randomized clinical trials. One member will be a biostatistician experienced in phase 2 and 3 oncology clinical trials, and none of the members will be Investigators in this study or employees of the sponsor.

Any AE that leads to a subject's treatment termination, and any serious adverse event (SAE) a subject experiences during the study, will be regularly reported to the DSMB, as specified in the Charter. The DSMB will receive unblinded data for any subject in the case of these safety events.

In addition, the study will be stopped in case clinical sepsis should occur, defined as one positive blood culture by PCR technique occur that could be attributed to sAGX0085 (stopping rule).

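### IMP-related adverse events arising between the end of short-term follow-up and the end of the study fall outside the protocol's late-event rule

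*Protocol*

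**What the plan says.** **Recording window.** Protocol 8, 8.4, 8.8 and Appendix D footnote h all end AE or SAE recording at the same point. In the words of 8.8, SAEs are collected "beginning from the signature of the ICF through the end of the short term follow-up phase". Protocol 7.3.5 puts that point at Day 42 (±3) after chemoradiation (CRT). Protocol 7.4 and Appendix D schedule only tumor status at Months 3, 6 and 12.

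**Late-event rule.** Protocol 8 adds one sentence for later events: "Any AE that occurs at any time after completion of the study, which the investigator considers to be related to" the study drug has to be reported. Protocol 12.9 fixes the reference date: "End of study is defined as the date when the last subject completes the long-term follow-up phase", which is 12 months after the last CRT dose. Protocol 11.5, written for financial disclosure, is consistent with it: "completion is defined as the date that the last subject has completed the protocol defined activities".

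**SAE notification.** Protocol 8.7 says that "the Sponsor must be notified immediately regarding any SAE that occurs after informed consent is obtained", and asks for all SAEs within 24 hours. Neither sentence has an end date.

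**DSMB.** Protocol 11.4 promises that "any SAE a subject experiences during the study, will be regularly reported to the DSMB, as specified in the Charter". SAP 4.3 repeats this.

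**Outputs.** Protocol 12.10 promises tumor response and updated safety information in an addendum after the second database lock. SAP 8.1 lists PK, tumor response, PD and genomics for the addendum and does not mention updated safety information. SAP 9 does not record this as a deviation.

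**The concern.** A late-event rule normally takes over where routine recording stops. Here it starts at the end of the study, with the whole long-term follow-up in between. Read literally, an event that the investigator attributes to AG013 need not be reported at Month 6 but must be reported after the study has ended.

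The stake is complete capture of product-related events. Protocol 3 says that this is the first use of AG013 together with concomitant CRT, and that subjects are followed to 12 months to check for an adverse effect on tumor response. Those are the months in which a related AE has no clear reporting route. Sample size, the primary analysis and error control are not affected.

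**Working it through.** **Length of the interval.** Inputs: the active phase ends on Day 14 post-CRT and short-term follow-up lasts 4 weeks (Protocol 3, Table 1); the final visit is at 12 months ±14 days (Protocol 7.4). Twelve months is taken as 365 days.

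- End of short-term follow-up: 14 + 4 × 7 = Day 42, as the protocol states. For 7 weeks of CRT, 49 + 42 = Day 91 from the start of CRT, which agrees with SAP 8.7.1.
- Nominal interval: 365 − 42 = 323 days, or 323/365 = 88% of the year after CRT.
- Shortest with visit windows: (365 − 14) − (42 + 3) = 306 days.
- Longest with visit windows: (365 + 14) − (42 − 3) = 340 days.
- With 12 months as 360 days, the nominal figure is 318 and the shortest is 301.
- Routine recording runs 42 − 14 = 28 days past the last IMP dose.

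These figures run to each subject's own 12-month visit. Because 12.9 dates study end by the last subject, the wait is longer for those enrolled earlier. It is shorter where follow-up is extended for persistent grade 2 or worse mucositis (Protocol 7.3.5).

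**Which rule reaches an event first arising at Month 6?**

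| Rule | Non-serious, IMP-related | Serious, IMP-related | Serious, unrelated |
|---|---|---|---|
| Recording window (8, 8.4, 8.8, footnote h) | No | No | No |
| Late-event sentence (8) | Not yet | Not yet | No |
| Notification (8.7) | Not applicable | Yes if literal, no if bounded | Yes if literal, no if bounded |
| Serious unexpected reactions; IMP-associated bacteremia and sepsis (8.10) | No | Yes, for these types | No |
| Tumor status (6.4) | No | Death, progression, new malignancy | Death, progression, new malignancy |

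**Reading 8.7.** Protocol 8 sends SAEs with onset up to the end of short-term follow-up to Sections 8.6 to 8.10, and the list of SAE information inside 8.7 repeats that end point. So 8.7 can be read as bounded. Its notification and 24-hour sentences do not say so themselves.

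**Reading the late-event sentence kindly.** Suppose study completion means each subject's own completion. Protocol 3 counts long-term follow-up as one of the four study periods, so a subject completes at Month 12 and the 323 days remain uncovered.

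The first column is therefore the clear gap. In the second, the late-event sentence does not yet apply and the answer turns on how 8.7 and 8.10 are read.

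**The case against.** The strongest case on the other side has four parts.

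1. Ending routine AE collection 28 days after the last dose is an ordinary choice. AG013 is an expectorated rinse, and the healthy-volunteer study found no evidence of systemic exposure (Protocol 1.2.2). This stands. The fault lies in where the late-event rule starts.
2. Protocol 8 opens by saying that AEs are recorded throughout the study. This stands in part: it arguably reaches a late related AE, but the next sentences limit recording to the short-term window.
3. Serious reactions are covered by 8.10, which has no end date. This largely stands, and it narrows the clear gap to non-serious events.
4. Few events will be affected. This is likely; the documents give no count, and none is claimed here.

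Three stronger readings are tempting, and the documents do not support them.

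- *Sections 8, 8.7, 8.8 and 11.4 are in open conflict over late SAEs, so sites will report differently.* The routing in Protocol 8 and the list inside 8.7 both point to the short-term window. The loose end is a missing end date in 8.7.
- *The DSMB will not receive late SAEs.* The promise in 11.4 is tied to the Charter, which is not among these documents and may set the period.
- *Late deaths and second primaries go unrecorded.* Protocol 8.4 excludes only mucositis-type events from AE recording ("Clinical symptoms or events such as mucositis or stomatitis are not to be recorded as an AE or SAE"), so a late death could raise the SAE question. It is captured in any case: 6.4 collects progression, second primaries, additional malignancies and survival; SAP 8.4 counts deaths by arm; SAP 8.8.2 lists long-term deaths with causes; and SAP 8.8.4 tabulates tumor response by arm.

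**Conclusion.** The point holds in limited form. As written, IMP-related AEs that first arise after short-term follow-up and before study end fall outside the late-event rule, for nominally 323 days per subject (306 to 340). Only the general opening of Protocol 8 arguably covers the non-serious ones. For SAEs, the matter is a missing end date in the notification sentences of 8.7. The addendum mismatch between Protocol 12.10 and SAP 8.1 is a smaller loose end of the same kind.

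This rests on 12.9 governing what completion of the study means and on 12 months being about 365 days; the kinder reading of completion leaves the same gap. The Charter and the German protocol version named in SAP 2 were not available and could change how late events are handled in practice. This is a safety-reporting correction worth making, with no bearing on the efficacy conclusions.

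**What to change.** 1. **Protocol 8:** in the late-event sentence, replace study completion with the end of short-term follow-up as the starting point. The rule then begins where routine recording stops.
2. **Protocol 8.7 and 8.8:** state that all SAEs are recorded and notified through the end of short-term follow-up, and that SAEs considered IMP-related are notified at any time after it.
3. **SAP 8.1:** add the updated safety information promised in Protocol 12.10 to the contents of the addendum.

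The cost is a few sentences and no new visit. Sites would have to report the few late events they judge IMP-related.

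Extending the reporting of all SAEs to Month 12 is optional and a matter of judgement. It would bring in mostly cancer-related events, each with the 24-hour notification and documentation that 8.7 requires, and much of the tumor and survival information is already collected under 6.4.

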8.1 Adverse Event Definition

An adverse event (AE) is any untoward medical occurrence in a subject administered an investigational product and which does not necessarily have a causal relationship with this treatment. An AE can be any unfavorable and unintended sign (e.g. an abnormal laboratory finding), symptom or disease temporally associated with the use of an investigational product, whether or not considered related to this investigational product. This includes an event that emerges during treatment having been absent pre-treatment or an event that worsens relative to the pre-treatment state. Recurrent symptoms of a chronic pre-existing condition are not considered AEs unless they occur in a worse or unexpected pattern during IMP administration.

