- Any SAE that is unexpected and related to AG013, results in hospitalization or prolongs an existing hospitalization, results in persistent or significant disability/incapacity, or is a congenital anomaly/birth defect will be reported to regulatory authorities within 15 days of receipt of the report. Some regulatory authorities may have alternative timelines for submission of suspected unexpected serious adverse reactions. In those cases, specific local requirements for submission of SAE reports will be applied.
- All SAEs will be followed until resolution or stabilization. Follow-up reports for SAEs reported as 7- 15-day reports will be submitted within the same time frame as the initial report.

Additionally, the IRB and/or IEC must be notified in writing of any unexpected, related SAEs or as required by the local IRB/IEC. It is the responsibility of the investigator/contract research organization (CRO) to notify the IRB/IEC.

If applicable, SAEs will be reported to the appropriate regulatory agencies by the Sponsor or designee. In case the local regulations require notification through the investigator, the Sponsor will facilitate this process.

The information to be recorded for SAEs should include the following:

This document contains confidential information. It is intended solely for the use of the principal investigator, co-investigators, staff, appropriate institutional review boards or ethical committees, and other required regulatory bodies.

- The onset of any new AE or the worsening of an observation documented from signature of the ICF through the end of the short term follow-up phase
- The specific type of event in standard medical terminology
- The duration of the clinical event (start and stop dates)
- The severity of the clinical event
- Seriousness (SAE) criteria
- Relevant laboratory and examination results
- Dosing schedule of IMP
- Indications and dosing schedules of concomitant medications
- Relationship of the AE to the IMP as defined in Section 8.3
- Management of IMP administration and other action taken to alleviate the clinical events
- Past medical and surgical history and concurrent diseases
- De-challenge/re-challenge results, if applicable
- The outcome of the clinical event

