10.6 Safety Analysis

Safety/tolerability analyses will be performed using data from the SAF analysis set. Safety will be evaluated on the basis of treatment-emergent AEs (TEAEs), vital signs, weight, physical examinations, and clinical laboratory assessments.

All adverse events will be coded by Preferred Term and System Organ Class using the most recent version of MedDRA. The National Cancer Institute Common Terminology Criteria for Adverse Events (CTCAE) (Version 4.03) will be used to grade both clinical and laboratory AEs. By-patient listings of deaths, SAEs, and AEs leading to discontinuation will be provided. The by-patient AE data listings will include onset and resolution dates, verbatim term, Preferred Term, treatment, severity (grade), relationship to treatment, action taken for the event, and outcome.

This document contains confidential information. It is intended solely for the use of the principal investigator, co-investigators, staff, appropriate institutional review boards or ethical committees, and other required regulatory bodies.

The incidence of treatment-emergent AEs (TEAEs) will be summarized by treatment group and tabulated by System Organ Class (SOC) and Preferred Term (PT). A TEAE is defined as an AE that first occurs or worsens in severity on or after the first dose of the IMP. TEAEs will be further summarized by severity (grade) and relatedness to IMP. Each AE (based on PT) will be counted only once for a given subject. If the same AE occurs on multiple occasions, the highest severity and strongest relationship will be assumed. If 2 or more AEs are reported as a unit, the individual terms will be reported as separate events.

Vital signs (systolic and diastolic blood pressure, pulse, and temperature) and body weight will be summarized for each treatment group using descriptive statistics. Summary statistics (n, mean, median, SD, minimum, and maximum) will be calculated for both the actual value and the change from baseline value at each scheduled visit.

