8.8.2 ADVERSE EVENTS

All AEs will be coded by PT and SOC using MedDRA version 19.0 or higher. The NCI-CTCAE (Version 4.03) will be used to grade both clinical and laboratory AEs.

The incidence of TEAEs will be summarized by treatment group and tabulated by SOC and Preferred Term (PT). A TEAE is defined as an AE that first occurs or worsens in severity on or after the first dose of the IMP until end of short term follow-up. Summary tables will include all TEAEs. Incomplete starting dates of AEs will be imputed using the rules from section 8.3 of this SAP. TEAEs will be further summarized by severity (grade) and relatedness to IMP. Each AE (based on PT) will be counted only once for a given

subject. If the same AE occurs on multiple occasions, the highest severity and strongest relationship will be assumed. If 2 or more AEs are reported as a unit, the individual terms will be reported as separate events. AE severity will not be imputed if missing.

Summaries and by-patient data listings of TEAEs, AEs leading to death, SAEs, and AEs leading to discontinuation will be provided. The by-patient AE data listings will include onset and resolution dates, verbatim term, PT, treatment, severity (grade), relationship to treatment, action taken for the event, and outcome. All the deaths, including those reported during the long-term follow-up period, will be listed with the primary causes.

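### Protocol 8.1 ties AE status for flares of chronic pre-existing conditions to the dosing period, which contradicts AE collection and TEAE windows that run to the end of short term follow-up

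*Protocol*

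**What the plan says.** Two rules sit next to each other in Protocol Section 8.1. The general rule counts as an AE "an event that worsens relative to the pre-treatment state", with no reference to when dosing ends. The next sentence carves out an exception: "Recurrent symptoms of a chronic pre-existing condition are not considered AEs unless they occur in a worse or unexpected pattern during IMP administration". Below, *flare* means a worse or unexpected recurrence covered by that exception.

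The other rules use a longer window:

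- Protocol Section 8 on collection: "All AEs with onset dates from signature of the ICF through the end of the short term follow-up phase will be recorded".
- Protocol Section 8.4 repeats that period, asks for all clinical events and adds: "The need to capture this information is not dependent upon whether the clinical event is associated with the use of any IMP".
- Protocol Section 8.7, in its list of SAE information, includes "the worsening of an observation documented from signature of the ICF through the end of the short term follow-up phase".
- Protocol Section 10.6 on analysis: "A TEAE is defined as an AE that first occurs or worsens in severity on or after the first dose of the IMP". It sets no stop at the last dose.
- SAP 8.8.2 counts an AE that "first occurs or worsens in severity on or after the first dose of the IMP until end of short term follow-up".

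IMP is planned to stop 14 days after the last day of CRT (Protocol 5.3). Short term follow-up then lasts four weeks (Protocol Section 3).

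**The concern.** The collection rule, both TEAE definitions and the SAE definition (Protocol 8.6) all operate on AEs. If Section 8.1 says an event is not an AE, the later rules have nothing to act on, and the SAP cannot recover an event that the site never entered.

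Two things are at stake. The first is safety endpoint 1, the incidence of AEs including SAEs (Protocol 10.1.3). The second is SAE handling. On the literal reading, a hospital admission for a chronic condition that worsens after the last dose is outside the SAE definition, and so outside 24-hour reporting (8.7) and the regular SAE reports to the DSMB (11.4). Two sites could each follow the protocol and record the same flare differently.

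The exception also makes the countable period depend on each subject's time on IMP. The TEAE summaries are per-subject incidences and no adjustment for exposure is described, so unequal periods would not be corrected.

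**Working it through.** **1. The rules side by side**

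| Rule | Start | End |
|---|---|---|
| Exception for flares (Protocol 8.1) | first IMP dose | last IMP dose |
| General worsening rule (Protocol 8.1) | pre-treatment state as reference | not tied to dosing |
| Collection (Protocol 8, 8.4) | consent | end of short term follow-up |
| TEAE (SAP 8.8.2) | first IMP dose | end of short term follow-up |

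The exception is the only rule that stops at the last dose. It also starts later than collection does, but events before the first dose are not treatment-emergent, so the front end does not affect TEAE counts.

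**2. Window length**

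Inputs from Protocol Section 3: active phase 7 to 9 weeks; short term follow-up Day 15 to Day 42 after CRT.

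- Days on IMP for a completer: 7 × 7 = 49 to 9 × 7 = 63.
- Days after the last dose: 42 − 14 = 28.
- Treatment-emergent window: 49 + 28 = 77 to 63 + 28 = 91 days. The upper figure agrees with the Day 91 that SAP 8.7.1 uses for the end of short term follow-up.

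**3. Share of the window outside the exception, literal reading**

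Share = 1 − (days on IMP) / (window).

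| Subject | 77-day window | 91-day window |
|---|---|---|
| Completer | 28/77 = 36% | 28/91 = 31% |
| Stops IMP Day 28, still followed | 49/77 = 64% | 63/91 = 69% |
| Stops IMP Day 14, still followed | 63/77 = 82% | 77/91 = 85% |

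The two stopping days are chosen for illustration.

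**4. What a difference in stopping could do (hypothetical)**

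The documents give no stopping rate by arm and no flare rate, so everything in this step is assumed.

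*Mean countable time.* 91-day window, stoppers leave IMP on Day 14, 20% of one arm and 10% of the other:

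- 0.8 × 63 + 0.2 × 14 = 53.2 days
- 0.9 × 63 + 0.1 × 14 = 58.1 days
- 53.2 / 58.1 = 0.916, about 8% fewer recorded flares at the same true rate.

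*Proportion with at least one flare.* With a constant hazard and a true proportion q over window W, the proportion seen in d days is P(d) = 1 − (1 − q)^(d/W). For q = 20% and W = 91:

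- P(63) = 14.3% and P(14) = 3.4%.
- 10% stopping: 0.9 × 14.3% + 0.1 × 3.4% = 13.2%.
- 20% stopping: 0.8 × 14.3% + 0.2 × 3.4% = 12.1%.
- Spurious difference: 1.1 percentage points.

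The assumptions were then varied: q of 10% to 30%, stopping of 10% v 20% or 10% v 30%, stop on Day 14 or 28, and either window. The spurious difference runs from about 0.3 to 3.3 points. Across those settings a true 20% is recorded as about 10% to 14%. With equal stopping in the two arms the difference is 0, but both arms still lose events.

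**The case against.** The strongest case on the other side is that Protocol Section 8 as a whole points sites toward recording these events. The sentence just before the exception covers worsening with no dosing limit, Section 8.4 asks for every clinical event, and Section 8.7 names worsening up to the end of short term follow-up. This stands to the extent that loss is not certain. It does not remove the problem, because a specific exception can reasonably be read as overriding the general rule before it.

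A reader might infer that all worsening after the last dose is dropped. The documents do not support that. The exception covers only flares of chronic conditions already present. New events and other worsening are unaffected, mucositis and stomatitis are not recorded as AEs at all (8.4), and graded laboratory worsening appears in shift tables (SAP 8.8.3).

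A reader might also infer that the arm with more early stopping will look safer. That needs different stopping rates, stoppers who stay under observation, and sites that decline to record the flares. The documents show none of these. For subjects removed from the study, safety follow-up happens only if possible (4.4), and new wording would not recover events missed for that reason.

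The primary safety objective covers only the active treatment phase, so a completer's 28 days fall outside it. That is correct, but it does not settle the matter. A subject who stops IMP early can still be within that phase, and the TEAE counts use the longer window.

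Finally, the AE summaries are descriptive and no safety test depends on them. That also stands, and it limits the severity.

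**Conclusion.** Wrong as written: an internal contradiction, of minor severity. The exception in Protocol 8.1 uses a shorter window than the collection rule and the SAP's TEAE rule. If a site follows it literally, flares after the last dose may go unrecorded as AEs and therefore as SAEs.

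The exposed period is 31% to 36% of the treatment-emergent window for a completer, and longer for an early stopper who is still followed. These are shares of time, not of events. Turning them into event counts needs flare rates that the documents do not give.

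The conclusion rests on the text and on the planned visit timing alone. No between-arm bias is established. The 8% figure and the range of 0.3 to 3.3 points are illustrations under assumed stopping rates, and apply only to this subset of AEs. The SAE consequence is a firmer reason to act, since it follows from the definitions without any assumption about stopping.

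**What to change.** In Protocol 8.1, replace the closing phrase of the exception, which limits it to the dosing period, with a reference to the AE collection period set in Section 8 (consent to the end of short term follow-up). Put the same rule in the eCRF completion guidelines so that sites apply it uniformly. The TEAE definition in SAP 8.8.2 needs no change.

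The cost is one phrase in the protocol, with the IRB/IEC approval that Section 12.2 requires for an amendment, and one line in the guidelines. The downside is slightly higher AE counts in both arms. Treatment and statistical methods are unaffected. For a completer, all 77 to 91 days of the treatment-emergent window would then count, in place of 49 to 63.
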